**Headache Impact Test (HIT-6)**

The Headache Impact Test (HIT-6) is a short-form self-administered questionnaire based on the Internet-HIT question pool. The HIT-6 was developed as a global measure of adverse headache impact to assess headache severity in the previous month and change in a patient's clinical status over a short period of time. Six questions cover:

- severe pain,
- limitation of daily activity (household, work, school and social),
- wanting to lie down when headache is experienced,
- feeling too tired to work or do daily activities because of headache,
- feeling fed up or irritated because of headache, and
- headache limiting ability to concentrate or work on daily activities.

The points are summed over six questionnaire items using special algorithm to produce a total HIT-6 score that ranges from 36 to 78. HIT-6 scores can be categorized into 4 grades, representing

- little or no impact (49 or less)
- some impact (50-55)
- substantial impact (56-59)
- severe impact (60-78)

due to headache. No recall period is specified for the first 3 items. The recall period is the past 4 weeks for the last 3 items.

Subjects complete the HIT-6 using the eDiary during their scheduled clinic visit. Please refer to [HIT-6 scoring](#) for scoring details.

**Short Form Health Survey Version 2, 4-week recall period (SF-36v2)**

The SF-36 is a widely used measure of health-related quality of life (HRQoL) among healthy subjects and patients with acute and chronic conditions. It consists of eight subscales that can be scored individually:

[figure not shown]
- Physical Functioning
- Role-Physical
- Bodily Pain
- General Health
- Vitality
- Social Functioning
- Role-Emotional

- Mental Health

Two overall summary scores, the Physical Component Summary (PCS) and the Mental Component Summary (MCS) also can be computed.

Subscale- and component summary scores are scaled to vary between 0 and 100 with 0 indicating worst possible health state and 100 best possible health state.

Calculation of SF-36 scores utilizes general population norm values. Scores are constructed to have an average value of 50 and a standard deviation of 10. Therefore, patients with the SF-36 scores below 50 have a health state below the average health state level of the general population. Patient's SF-36 score values below 40 may indicate impaired health state. Please refer to [SF-36v2 scoring](#) for scoring details.

### 2.1.1.5 Safety Endpoints

Analyses on Adverse Events will be performed for the entire study without differentiating between the DBTE and Follow-up epoch. Independently, whether a patient is an ASA-patient or not, AEs will be analysed in the following analysis window:

[Study Day 1; EoS Date]

Remaining safety analyses will be performed for the DBTE and Follow-up Epoch separately. Laboratory, vital signs, ECG and C-SSRS are assessed during study visits and, therefore, will be assigned to the DBTE based on (Table 2.1.1.2-1).

Concomitant medications will be assigned to the DBTE based on the following analysis window:

[Study Day 1; Week 24 visit date if the visit was performed / MIN(EoS, study day 169) if the visit was not performed]

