5.5.4 Instructions for prescribing and taking study treatment

The investigational product dose is either 70 mg or 140 mg depending on the investigators decision, which has to be made for each patient individually and in accordance with the product information: the recommended dose is 70 mg, some patients may benefit from 140 mg (see Section 5.1 of AIMOVIG® SmpC).

In case of insufficient response, the dose may be escalated from 70 mg to 140 mg. Possible reasons for up titration could be, but are not limited to:

- insufficient response as deemed by physician and/or patient
- reduction of acute medication use not satisfactory
- insufficient improvement in life quality

An adjustment of the 70 mg dose to 140 mg can be performed at any time during the DBTE. The investigational product dose of 140 mg must not be changed once a patient received the dose during DBTE.

Reference treatment doses are determined during the uptitration phase and must aim to reach the recommended daily treatment dose of 100 mg topiramate in accordance to the German SmPC. The reference treatment dose established during the up titration phase must not be changed during the 18-week maintenance phase.

There are no temporal restrictions for the investigational or the reference treatment (e.g., proximity to meals, sleep or activity).

Test-IMP:

70 mg and 140 mg erenumab or respective placebos will be administered by qualified study staff at each dosing visit during the 24 week double-blind treatment epoch (i.e., at Day 1 and Week 4, Week 8, Week 12, Week 16 and Week 20). Subcutaneous (s.c.) injections are to be given for each investigational product administration. For purposes of study treatment dosing, “q.m.” refers to an every 4 weeks injection regimen. The study drug administration date should be in 4 week increments (+/- 4 days) from the first dose of study drug. Any dose administrations that may occur greater than +/- 4 days from the 4 week time point (e.g., patient unavailability) should be discussed with the Sponsor prior to dosing. The anatomical sites for administration of investigational product are the upper arm, upper thigh, or abdomen; the location of the injection site should be documented in the source document. In order to reduce irritation at the injection site, the investigational product should be stored at room temperature for 30 minutes prior to the administration.

Control-IMP:

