5.6.2 Discontinuation of study treatment

Discontinuation of study treatment for a patient occurs when study drug is stopped earlier than the protocol planned duration, and can be initiated by either the patient or the investigator.

The investigator must discontinue study treatment for a given patient if, on balance, he/she believes that continuation would negatively impact the risk/benefit of trial participation.

Study treatment must be discontinued under the following circumstances:

- Patient wish
- Pregnancy (see Section 6.5.6 and Section 7.5)
- Use of prohibited treatment as per recommendations in Table 5-1
- Any situation in which study treatment might result in a safety risk to the patient
- Any laboratory abnormalities that in the judgment of the investigator, taking into consideration the patient's overall status, prevents the patient from continuing participation in the study

If discontinuation of study treatment occurs, the patient should NOT be considered withdrawn from the study, and should continue recording in the eDiary as per protocol. Also, patients who discontinued treatment from the double-blind treatment epoch will follow the abbreviated visit schedule until the follow up visit (week 28) is reached (Table 6-2). These visits should be performed with all assessments outlined in Table 6-2. At a minimum, the following data should be collected at clinic visits or via telephone visits:

- new/concomitant treatments
- adverse events / serious adverse events

If the patient cannot or is unwilling to attend any visit(s), the site staff should maintain regular telephone contact with the patient, or with a person pre-designated by the patient. This telephone contact should preferably be done according to the study visit schedule.

Patients who prematurely discontinue the study for any reason should be scheduled for a visit as soon as possible, at which time all of the assessments listed for the final visit (Visit 199) will be performed. At this final visit, the adverse event and concomitant medications should be reconciled on the eCRF. Patients will return for a follow-up visit approximately 8 weeks after their last dose of study medication, and perform the study procedures outlined in Table 6-1.

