5.6.5 Early study termination by the sponsor

The study can be terminated by Novartis at any time for any reason. This may include reasons related to the benefit-risk assessment of participating in the study, practical reasons, or for regulatory or medical reasons (including slow enrollment). Should this be necessary, the patient must be seen as soon as possible and treated as a prematurely withdrawn patient. The investigator may be informed of additional procedures to be followed in order to ensure that adequate consideration is given to the protection of the patient's interests. The investigator will be responsible for informing the Institutional Review Board / Independent Ethics Committee (IRBs/IECs) of the early termination of the trial.

6 Visit schedule and assessments

Table 6-1 and Table 6-2 list all of the assessments and indicate with an "X" when the visits are performed.

Patients must be seen for all visits on the designated day, or as close to it as possible. Missed or rescheduled visits should not lead to automatic discontinuation.

During visits 102 to visit 107, intervals between visits must not exceed 7 +/- 1 day calculated from Visit 101 (Day1), to ensure continuous supply regarding oral medication.

During visits 108 to visit 199, intervals between visits should not exceed 28 +/- 4 days calculated from Visit 101 (Day 1). If the visit has to be scheduled outside this window, an approval from the sponsor has to be collected to ensure continuous supply of oral medication and patient safety regarding s.c. medication.

	Screen	Baseline	Double – Blind Treatment Epoch (Titration)						Double – Blind Treatment Epoch (Maintenance)						Follow Up ²
Visit number ¹	0	1	101	102	103	104	105	106	107	108	109	110	111	199	201
End of Week	-6	-4	0	1	2	3	4	5	6	8	12	16	20	24	28
Day	-42	-28	1	8	15	22	29	36	43	57	85	113	141	169	197
Baseline Phase Completion form		x													
Double-Blind Treatment Phase Completion form														x	
Follow-Up Phase Completion form															x

- 1 – All study visit target dates are to be calculated from the Day 1 visit date and all study procedures for a given visit should be completed on the same day.
- 2 – The Follow-Up Visit is required 8 weeks after last IMP injection (erenumab / corresponding Placebo) for patients who discontinue the study or 4 weeks after V199 for patients who complete the study. The Follow-Up visit can be skipped if any other safety follow up visit occurred 8 weeks after last IMP injection.

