**2.1.1.2 Visit and analysis window**

Since the actual visit for a subject may not exactly coincide with their targeted visit date, the actual visit date is mapped to a study visit.

The nearest study day window will be utilized to define study visit for lab, vital signs, ECG, C-SSRS and some PROs collected during office visits (HIT-6, SF-36v2, ██████████) before dose is administered.

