## **2.8 Safety analyses**

Safety analyses will be based on safety data set (SAF).

All safety analyses will be performed for the Double-Blind Treatment Epoch and Follow-up Epoch separately and in descriptive manner.

Missing data will not be imputed for safety endpoints.

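### As written, the SAP's study-day windows put the follow-up visit of a patient who leaves the study early into the double-blind safety tables, unless the last injection was at Week 20

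*SAP*

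**What the plan says.** SAP 2.1.1.5 treats adverse events over one window for the whole study. For everything else it says: "Remaining safety analyses will be performed for the DBTE and Follow-up Epoch separately". SAP 2.8 repeats the principle ("All safety analyses will be performed for the Double-Blind Treatment Epoch and Follow-up Epoch separately"), and SAP 2.8.4.3 applies it to C-SSRS.

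The assignment rule follows in SAP 2.1.1.5: these measurements "are assessed during study visits and, therefore, will be assigned to the DBTE based on (Table 2.1.1.2-1". That table belongs to SAP 2.1.1.2, which gives the mapping method: "The nearest study day window will be utilized to define study visit for lab, vital signs, ECG, C-SSRS". Its windows run without a gap from day 1 to day 182. It has no row for follow-up, and neither section mentions visit number, early exit or treatment status. No sentence says how a record enters the Follow-up Epoch.

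The protocol defines follow-up by visit. Section 3.5 identifies the Follow-Up Epoch by V201/V201-ASA, and Table 6-1 puts V201 in the follow-up column. The date of V201 depends on how the patient finished. Footnote 2 of Table 6-1 states: "The Follow-Up Visit is required 8 weeks after last IMP injection (erenumab / corresponding Placebo) for patients who discontinue the study"; completers attend 4 weeks after V199. Section 5.6.2 uses a different anchor for patients who leave the study: "Patients will return for a follow-up visit approximately 8 weeks after their last dose of study medication". Patients who stop treatment but stay in the study follow the abbreviated schedule, with follow-up at week 28.

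**The concern.** The SAP sorts records into the DBTE by date, while the protocol sets an early leaver's follow-up visit by time since the last injection. Injections are 4 weeks apart and that visit comes 8 weeks after the last one, so it can fall on a day that the SAP labels as a double-blind visit.

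What is at stake is the correctness of the by-visit, by-epoch safety tables: change from baseline in laboratory values (SAP 2.8.3) and vital signs (SAP 2.8.4.2), and, where C-SSRS is collected at V201, the by-visit counts and the shift in maximum severity (SAP 2.8.4.3). A misassigned record appears under a DBTE week and is missing from the follow-up summary, which is where the protocol's definition puts it.

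**Working it through.** This is date arithmetic; no sample size or error rate is involved.

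**Inputs**
- Injections (Protocol 5.5.4): "at Day 1 and Week 4, Week 8, Week 12, Week 16 and Week 20", that is days 1, 29, 57, 85, 113 and 141. Tolerance: "The study drug administration date should be in 4 week increments (+/- 4 days) from the first dose of study drug".
- V201 for a patient who discontinues the study (Table 6-1, footnote 2): last injection + 56 days.
- DBTE windows (SAP Table 2.1.1.2-1): Week 8 = days 50–70, Week 12 = 71–98, Week 16 = 99–126, Week 20 = 127–154, Week 24 = 155–182.

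**Reproducing the plan's own figure.** Table 6-1 gives V201 as day 197. From V199: 169 + 28 = 197. From the Week 20 injection: 141 + 56 = 197. Both agree.

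**Early study leavers, injection anchor**

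| Last injection (day) | V201 = day + 56 | Label under the SAP rule |
|---|---|---|
| 1 | 57 | Week 8 |
| 29 | 85 | Week 12 |
| 57 | 113 | Week 16 |
| 85 | 141 | Week 20 |
| 113 | 169 | Week 24 |
| 141 | 197 | none |

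Five of the six last-injection visits fall in a DBTE window, each exactly on its target day. A shift of 4 days either way changes no label: day 117 gives 173 (still Week 24), and day 137 gives 193 (still outside).

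**Other anchor (Protocol 5.6.2, last dose of study medication).** V201 falls inside the windows when last dose + 56 ≤ 182, so when the last dose is on or before day 182 − 56 = 126. A patient last injected on day 113 who took tablets beyond day 126 would fall outside.

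**Patients not affected**
- Completers: V199 on days 165–173 gives V201 on days 193–201, outside all windows.
- Patients who stop drug but stay in the study: follow-up at week 28, target day 197, outside.
- Leavers after the Week 20 injection: day 197, outside.
- Patients who withdraw consent: no further visits (Protocol 5.6.3).

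**Which data are involved.** Protocol 6.5.4.2 confirms chemistry at V201. The assessment rows of Table 6-1 were not readable in the text available to me, so vital signs at V201 rest on the V201-ASA column of Table 6-2. C-SSRS rests on Protocol 7.6, which requires it at every visit, although Table 6-2 does not mark it at V201-ASA. ECG is not marked there either and is left out of this point.

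**Effect on chemistry rows.** Protocol 6.5.4.2 schedules DBTE chemistry at V101, V108 (Week 8) and V199 (Week 24) only. Relabelled values therefore mix with scheduled ones at Weeks 8 and 24. At Weeks 12, 16 and 20 they would form sparse rows with no scheduled counterpart, alongside any early-exit or unscheduled samples.

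**The case against.** The strongest reply is that the intent is plain. Table 2.1.1.2-1 is headed as covering the DBTE, SAP 2.1.1.2 presents the windows as a way to handle visits that miss their target date, V201 is a separately numbered visit with its own completion form, and separate epochs are required more than once. A programmer could filter on V201, and the table shells, which were not available to me, may say so. The point about intent stands. But the only written rule works by date and gives the opposite result, and a CRO executes the analysis, so the SAP should state the condition.

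A second reply also stands: the DBTE in this SAP is not an on-treatment period. Patients who stop drug remain on the abbreviated schedule, and their off-drug values at V105-ASA to V199-ASA are DBTE data by design.

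A reader might go further and infer that off-drug values contaminate the topiramate arm more, because topiramate is expected to be stopped more often, and so dilute a reversible drug effect there. The documents do not support this. Stopping treatment leads to the abbreviated schedule with follow-up at week 28, outside the windows; only leaving the study and still attending V201 creates the problem. No rate of study exit is given for either arm. Off-drug abbreviated-schedule values would also remain in the DBTE tables after the correction.

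**Conclusion.** The rule is wrong as written, and the consequence is limited. Followed literally, it labels V201 as a DBTE visit for any patient who discontinues the study, attends V201 8 weeks after the last injection, and had that injection at Week 16 or earlier. If the visit is timed from the last dose of study medication instead, the same holds for a last dose on or before day 126. This conflicts with the SAP's separate-epoch reporting and with the protocol's definition of follow-up by visit.

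Five of six counts last-injection visits, not patients. The number of patients affected is not in the documents, V201 can sometimes be skipped (Table 6-1, footnote 2), and a difference between arms is not established. Only descriptive tables of laboratory values, vital signs and, where collected, C-SSRS are touched. Adverse events are analysed over one window, and the primary and secondary endpoints do not use these windows.

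**What to change.** State in SAP 2.1.1.2 and 2.1.1.5 that V201 and V201-ASA records belong to the Follow-up Epoch by nominal visit, whatever the study day. State also that the day windows apply only to DBTE visits, including early-exit Visit 199 assessments, unscheduled visits before V201, and V105-ASA to V199-ASA. With this rule none of the six last-injection times puts V201 in a DBTE window, and the difference between the two protocol anchors no longer affects epoch assignment.

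The cost is a short addition to the SAP, one programming condition and a check of the table shells; no new data are needed. The change corrects epoch labelling. It does not turn the DBTE tables into on-treatment tables, and the SAP should not describe them as such.

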#### **Discontinuation of treatment due to AE during the DBTE**

Discontinuation of treatment due to AE during the DBTE is determined by the flag on the Treatment Completion eCRF page. "Death" as a reason for treatment discontinuation will be also included in AEs leading to treatment discontinuation.

#### **Treatment-Emergent Adverse Event (TEAE)**

Treatment emergent adverse events are defined as AEs occurred on or after the first dose of study treatment. AEs registered prior and after the first dose of study treatment are considered

as treatment emergent if they have increased severity based on preferred term any time after the first dose of study treatment.

In case of missing data on a day of AE start date, the AE is considered as treatment emergent if

$$\text{date of first dose of study treatment} \leq \text{latest possible start date}$$

Please, see [AE and Concomitant medication date imputation](#) for “latest possible start date” definition.

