- 3 – Including prior prophylactic medication.
- 4 – Includes blood pressure, pulse and temperature.
- 5 – Patient brings to each visit for use at site
- 6 – To be completed during applicable study visits before study drug administration, where applicable.
- 7 – Should also be performed at unscheduled visits.
- 8 – SAEs will be collected after signing of the informed consent through the end of the Follow-Up Epoch (8 weeks after the last IMP injection). Non-serious AEs will be collected after randomization (Visit 101) through the end of the Follow-Up Epoch (8 weeks after the last IMP injection).
- 9 – Study drug is administered by study staff, during the applicable study visits, q.m., s.c..
- 10 – Oral study drug will be dispensed to the patient at the center during the applicable study visit for home application.
- 11 – Sites will access the Interactive Response Technology (IRT) System to register study early termination.
- 12 – Should be additionally performed at any visit if deemed necessary by the investigator due to AEs.
- 13 – Should be performed/registered by the investigator prior to dosing during DBTE.
- TD = Treatment discontinuation; PFS = Prefilled syringe; PSD = Premature subject discontinuation; X = Assessment to be recorded in the source documents and the clinical data base; S = Assessment to be recorded as source documentation only.

Table 6-2 Abbreviated schedule of assessments (ASA) for patients with Treatment Discontinuation (TD)

Visit number	V105-ASA	V108-ASA	V109-ASA	V110-ASA	V111-ASA	V199-ASA	V201-ASA ²
End of Week¹	4	8	12	16	20	24	28
Complete Physical Exam						S	
Brief Physical Exam	S	S	S	S	S		
Weight						X	X
Vital Signs ³	X	X	X	X	X	X	X
Chemistry/Hematology ¹²		X				X	X
Serum Pregnancy						X	
Urine pregnancy	S	S	S	S	S		X
ECG						X	
Clinical Outcomes (eDiary)	eDiary should be maintained						
SF-36 ⁴ (eDiary)	X	X	X	X	X	X	
HIT-6 ⁴ (eDiary)	X	X	X	X	X	X	
C-SSRS	X	X	X	X	X	X	
Concomitant Medications	X	X	X	X	X	X	X
Adverse Events ⁵	X	X	X	X	X	X	X
Serious Adverse Events ⁵	X	X	X	X	X	X	X
Follow Up Phase Completion form							X

1 – All study visit target dates are to be calculated from the Day 1 visit date, and all study procedures for a given visit should be completed in the same day.

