7.1 Adverse events

An adverse event (AE) is any untoward medical occurrence (e.g., any unfavorable and unintended sign [including abnormal laboratory findings], symptom or disease) in a patient or clinical investigation patient from randomization (Visit 101) until the end of study visit (16 weeks after the last IMP injection). Any events occurring during the Screening and Baseline Epochs and conditions that were already present at the time of informed consent should be documented as medical history. An AE may or may not be temporally or causally associated with the use of a medicinal (investigational) product.

In addition, all reports of intentional misuse and abuse of the product are also considered an adverse event irrespective if a clinical event has occurred.

The occurrence of adverse events must be sought by non-directive questioning of the patient at each visit during the study. Adverse events also may be detected when they are volunteered by the patient during or between visits or through physical examination findings, laboratory test findings, or other assessments.

Abnormal laboratory values or test results constitute adverse events only if they fulfill at least one of the following criteria:

- they induce clinical signs or symptoms,
- they are considered clinically significant,
- they require therapy.

Clinically significant abnormal laboratory values or test results must be identified through a review of values outside of normal ranges/clinically notable ranges, significant changes from baseline or the previous visit, or values which are considered to be non-typical in patient with underlying disease. Investigators have the responsibility for managing the safety of individual patient and identifying adverse events. Alert ranges for laboratory and other test abnormalities are included in Appendix 1.

Adverse events must be recorded in the Adverse Events eCRF under the signs, symptoms or diagnosis associated with them, accompanied by the following information:

- the severity grade
 - mild: usually transient in nature and generally not interfering with normal activities
 - moderate: sufficiently discomforting to interfere with normal activities
 - severe: prevents normal activities
- its relationship to the study treatment
 - Yes
 - No

- its duration (start and end dates) or if the event is ongoing an outcome of not recovered/not resolved must be reported.

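### Every AE from first dose to end of study is tabulated as treatment-emergent, with no on-treatment counterpart, so the descriptive AE tables mix on-drug and off-drug time, unequally if the arms stop at different rates

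*SAP*

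**What the plan says.** - **Definition.** SAP 2.1.1.5: "Treatment emergent adverse events are defined as AEs occurred on or after the first dose of study treatment". A second sentence adds earlier events that worsen after first dose. No end date tied to last dose is given. Protocol 9.5.1.1 is open-ended in the same way.
- **Window.** The same SAP section runs AEs from Study Day 1 to the EoS date: "Independently, whether a patient is an ASA-patient or not, AEs will be analysed in the following analysis window".
- **Follow-up after stopping.** Protocol 5.6.2: "patients who discontinued treatment from the double-blind treatment epoch will follow the abbreviated visit schedule until the follow up visit (week 28) is reached". AEs are collected at each of the visits in Table 6-2, and Protocol 7.1 ties ascertainment to visits: "The occurrence of adverse events must be sought by non-directive questioning of the patient at each visit during the study".
- **Tables.** SAP 2.8.1 builds all its AE summaries from treatment-emergent events, as numbers and percentages of patients. The subject-incidence definition in 2.1.1.5 divides patients with an event by patients entering the period. Exposure durations are defined (2.1.1.5) and summarised (2.4.1), but no AE table uses them.
- **Epochs.** SAP 2.1.1.5: "Analyses on Adverse Events will be performed for the entire study without differentiating between the DBTE and Follow-up epoch". SAP 2.8: "All safety analyses will be performed for the Double-Blind Treatment Epoch and Follow-up Epoch separately and in descriptive manner".
- **End of AE collection.** Table 6-1 footnote 8 gives 8 weeks after the last injection, Table 6-2 footnote 5 gives V201-ASA, and Protocol 7.1 gives 16 weeks after the last injection.

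**The concern.** A patient who stops in Week 6 and has an AE in Week 27 is counted as having a treatment-emergent AE on the assigned drug. The primary hypothesis is that AE-related stopping differs between the arms, so the amount of off-drug time in the AE tables may differ too. Those tables support the tolerability account around the primary result. As planned, they cannot show how much of an arm's AE experience arose on drug, and they would understate an on-drug difference in the arm that stops more.

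**Working it through.** The plan has no figure of its own to reproduce here, because the readable text gives no stop rate and no expected AE rate. The calendar can be checked: day = 7 × week + 1 reproduces the target days in Table 6-1 (Week 4 = Day 29, Week 24 = Day 169, Week 28 = Day 197).

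**One early stopper.** Assume a stop at Week 6, last injection at Week 4 (Day 29), one taper week, and follow-up to Week 28. The SAP's exposure rule for the syringe gives 29 + 27 = Day 56, the end of Week 8. Tablets including taper end at Week 7. The later is Week 8, so 28 − 8 = 20 weeks are off drug, and 20/28 = 71.4% of the window.

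**Arm level.** Share = d × 20/28, with d the assumed stop fraction:
- d = 0.30: 21.4%
- d = 0.10: 7.1%

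Completers also have up to 4 off-drug weeks in both arms (last injection Day 141; 141 + 27 = Day 168). Adding (1 − d) × 4/28 gives 21.4 + 10.0 = 31.4% against 7.1 + 12.9 = 20.0%.

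**Range.** Counting simply from the stop at week s, with no allowance for injection interval or taper, share = d × (28 − s)/28:

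| d (assumed) | s = 3 | s = 6 | s = 12 |
|---|---|---|---|
| 5% | 4.5% | 3.9% | 2.9% |
| 10% | 8.9% | 7.9% | 5.7% |
| 20% | 17.9% | 15.7% | 11.4% |
| 30% | 26.8% | 23.6% | 17.1% |
| 40% | 35.7% | 31.4% | 22.9% |

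**Dilution.** Take an uncommon AE at twice the background rate on topiramate, and at background on erenumab and off drug (assumptions). With no early stops, the risk ratio to Week 28 is about (24 × 2 + 4)/28 = 52/28 = 1.86. If 30% of topiramate patients stop at Week 6, their risk is proportional to 6 × 2 + 22 = 34. The arm becomes 0.7 × 52 + 0.3 × 34 = 46.6, and the ratio falls to 46.6/28 = 1.66.

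**Splitting by epoch does not solve it.** Under SAP 2.8 the treatment epoch would be tabulated alone, but the Week 6 stopper stays in it to Week 24. The off-drug share is d × 16/24, that is 20.0% versus 6.7%.

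**A shorter window with crude percentages would be worse.** Assume identical hazards of 0.05 per week in both arms, stops at Week 3 in 30% versus 10%, and an illustrative cut four weeks after the stop.
- SAP window: 1 − exp(−0.05 × 28) = 75.3% in both arms, ratio 1.00.
- Stoppers under the cut: 1 − exp(−0.05 × 7) = 29.5%.
- Arm with 10% stopping: 0.9 × 75.3 + 0.1 × 29.5 = 70.8%.
- Arm with 30% stopping: 0.7 × 75.3 + 0.3 × 29.5 = 61.6%.
- Ratio 0.87, a false advantage for the arm that stops more.

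**Visit schedule.** The regular schedule has visits at Weeks 1 to 6, 8, 12, 16, 20, 24 and 28 (12). The abbreviated one has Weeks 4, 8, 12, 16, 20, 24 and 28 (7). They differ only at Weeks 1, 2, 3, 5 and 6.

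| Stop at week | 1 | 2 | 3 | 4 | 5 | 6 or later |
|---|---|---|---|---|---|---|
| Scheduled visits lost | 4 | 3 | 2 | 2 | 1 | 0 |

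**End of collection.** For the Week 6 stopper with a Week 4 injection, the three statements give Week 4 + 8 = 12 (Table 6-1 footnote), Week 28 (Table 6-2 footnote) and Week 4 + 16 = 20 (Protocol 7.1). The shares above use Week 28, as Table 6-2 covers patients off drug.

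**The case against.** **The window is a valid choice.** It gives both arms the same scheduled follow-up and fits the protocol's stance, in 9.3.1, of comparing arms whether or not patients adhere. With equal hazards it shows no difference, whereas a cut window with crude percentages invents one. This stands, and is why the existing tables should be kept. It does not justify calling them treatment-emergent or leaving out an on-treatment view.

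**Other outputs help.** SAP 2.8.1 also tabulates treatment-related AEs and AEs leading to discontinuation, all AEs are listed, and exposure is summarised by arm. This stands in part. The relatedness flag is an investigator's judgement on each event and supplies neither a risk window nor a denominator.

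**The size is assumed.** This stands. The calculation also supposes that every stopper stays to Week 28; for anyone who leaves earlier the window closes at EoS.

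**A reader might infer that patients off drug are questioned much less, so their AEs are under-recorded.** The documents do not support this for most of the time at issue. Only stops before Week 6 lose scheduled visits, and only within titration; the Week 6 stopper above loses none, and the schedules match from Week 8. Protocol 5.6.2 adds an unscheduled AE visit after taper for patients who had been on 75 or 100 mg, although it also allows minimum contact by telephone. The schedule is a minor point, relevant mainly to stops early in titration.

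**Exposure-adjusted rates have limits of their own.** They assume roughly constant hazards. If AEs cluster in titration, they overstate the arm with shorter exposure. This stands and belongs in the SAP text.

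**Conclusion.** The point holds as one of labelling and of a missing analysis. The SAP tabulates AEs that may arise months after the last dose as treatment-emergent, and has no on-treatment split or person-time in its AE sections. Early stoppers' off-drug time is 21.4% versus 7.1% of the AE window under the stated assumptions (30% versus 10% stopping at Week 6 after a Week 4 injection, all followed to Week 28), and about 3% to 36% of an arm's follow-up over the wider assumed range. Whether the imbalance is large in this trial cannot be read from the documents.

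A reader might also infer that the primary comparison is compromised. It is not: SAP 2.1.1.5 takes that endpoint from the flag on the Treatment Completion eCRF page, which the treatment-emergent rule does not touch. Only descriptive AE tables are affected.

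**What to change.** 1. Keep the Study Day 1 to EoS tables in SAP 2.8.1, but label them whole-study AEs.
2. In SAP 2.1.1.5, flag each AE as on-treatment or post-treatment. On-treatment would run from first dose to the later of last syringe date + 27 days and last tablet date including taper, with the same rule in both arms. Because one set of syringes or tablets is placebo in each arm, this can count some drug-free weeks as on-treatment; say so.
3. Add on-treatment tables by SOC and PT with patient-years and exposure-adjusted incidence per arm. Do not use crude percentages on the shortened window.
4. Reconcile SAP 2.1.1.5 with 2.8 on pooling or separating epochs for AEs, and reconcile the ends of AE collection in the Table 6-1 footnote, the Table 6-2 footnote and Protocol 7.1.

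The cost is SAP wording, one more set of tables and a protocol clarification; SAP 2.1.1.1 already defines the dosing dates. The downsides are more output and the constant-hazard assumption, so the adjusted rates must be read beside the whole-study tables, which also carry late-onset effects.
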